3. STUDY PROCEDURES

- Patients who are seen in clinic for rotator cuff pathology will undergo treatment for their rotator cuff based

on a shared decision-making process with the orthopedic surgeon, irrespective of this study. Once a treatment plan is in place, the patient will be introduced to this study and presented with the opportunity to participate. If the patient agrees, a formal consent process will take place in clinic and the patient will undergo initial, baseline testing of strength, range of motion, pain scores, and patient reported outcome scores.

Therefore, patients will be either in the nonoperative arm or the operative arm of this study. Within each arm, patients will be randomized via computer to be placed in either the blood flow restriction (BFR) cohort or the traditional (non-BFR cohort). Patients will prospectively undergo rotator cuff rehabilitation using BFR or conventional therapy by physical therapists with extensive experience in rotator cuff rehabilitation who will undergo training on use of BFR.

The nonoperative group will be given identical rehabilitation protocols, with the only difference being the use of a BFR cuff during rehabilitation for the BFR cohort. Similarly, the operative group will be given identical rehabilitation protocols, with the only difference being the use of a BFR cuff during rehabilitation for the BFR cohort.

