Throughout this protocol patients will have a pre-operative visit, an early 2 week post operative visit to check range of motion and wound healing, a six week visit to monitor range of motion and potentially clear for active ROM and sling discontinuation, and a three month visit prior to clearance to being return to more aggressive activity. Strength and range of motion will be recorded at each of these visits in order to assess the primary endpoint.

Outcomes:

Primary Outcome:

- Strength to be measured via dynamometer at each clinic visit

Secondary Outcomes:

- Range of motion via goniometer
- Pain via visual analogue scale (VAS) pain scale at each visit
- Patient reported outcomes scores at each visit
- Fatty infiltration and muscle atrophy measured via ultrasound and compared to pre-operative imaging

Plan to recruit patients starting in June 2020. Will enroll patients and collect data from June-2020 to May 2021. Manuscript writing and submission to occur in June 2021.

Data analysis: The primary endpoint of this study was a maximum repetition total work deficit of 15% between the BFR and control group as measured by dynamometer. This was based on previous data showing that a strength deficit of 15% represents a clinically significant difference that is not likely attributable to limb dominance. Work deficit was calculated in each group by comparing the operative leg with the nonoperative leg to obtain a deficit percent. A power analysis was performed before the study to assess the number of patients needed to detect a 15% total work deficit between the BFR and control groups. With a power of 80% (beta level $\frac{1}{4} 0.80$, alpha level $\frac{1}{4} 0.05$), a sample size of 34 (17 patients per group) was obtained. Data will be provided to and analyzed by trained statisticians to determine differences in primary and secondary outcomes.

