All continuous data will be analyzed using independent 2-group t tests and reported as means \pm standard deviations. Categorical data will be compared between the 2 groups using chi-square tests and reported as counts and percentages. A preliminary test to confirm the quality of variances will be conducted prior to utilizing the t test to confirm the appropriate statistical analysis. Nonparametric equivalents Wilcoxon rank-sum and Fisher exact tests will be used as needed for nonnormal distributions and low variable numbers, respectively. A multivariable regression analysis was performed to assess potential confounding demographic variables.

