10. WITHDRAWAL OF SUBJECTS

- Subjects will be withdrawn from the study if they are unable to tolerate the BFR therapy. Additionally, if they suffer from any complications of the therapy they will be withdrawn immediately. This will be facilitated by describing the reasons for withdrawal to the patient prior to initiating the study and ask patients and other providers to inform the investigators if there are any issues or concerns.

- Data collection on patients who were withdrawn will be terminated and data destroyed.
- Patients may withdraw from the study at any time for any reason without affecting the quality of their care

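### The t test is gated on an unspecified variance pre-test; if the BFR group shrinks and variances differ, the error rate can drift modestly from 5%, and prespecifying Welch avoids this at almost no cost

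*Combined protocol and SAP*

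**What the plan says.** All from the combined protocol and SAP.

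- **Section 3, data analysis, main test:** "All continuous data will be analyzed using independent 2-group t tests". Pooled or Welch is not stated.
- **Section 3, gate:** "A preliminary test to confirm the quality of variances will be conducted prior to utilizing the t test". I read the word before "of variances" as a slip for equality. The test, its level and the action on rejection are not given.
- **Section 3, fallbacks:** "Nonparametric equivalents Wilcoxon rank-sum and Fisher exact tests will be used as needed for nonnormal distributions and low variable numbers, respectively". Neither is tied to unequal variances.
- **Section 3, sample size:** 34 patients, 17 per group, to "detect a 15% total work deficit between the BFR and control groups", with 80% power and alpha 0.05. No SD is given.
- **Section 3, allocation:** "Within each arm, patients will be randomized via computer". The arms are operative and nonoperative. No blocking is stated.
- **Section 10:** "Subjects will be withdrawn from the study if they are unable to tolerate the BFR therapy". Data on withdrawn patients are destroyed.

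**The concern.** A variance pre-test protects the t test only if it finds the variance differences that matter. With 10 to 17 patients in a group it often does not, and the pooled test is then used where it does not fit.

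With equal groups this hardly matters, because the pooled standard error is still correct. With unequal groups it is wrong in a direction set by which group is the more variable. The plan has two routes to unequal groups. The intolerance rule can remove BFR patients only, and unblocked randomisation need not give equal numbers.

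At stake is the accuracy of the p-value and interval for strength and for any other continuous outcome where both conditions hold. Separately, leaving the pre-test and its consequence undefined allows the primary test to be chosen after the data are seen.

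**Working it through.** **1. The plan's own figure.** No SD is stated, so 17 per group cannot be verified. With an assumed SD of 15 points (standardised difference 1.0), the normal formula gives n = 2 × (1.960 + 0.842)² × (15/15)² = 15.7, so 16 per group. The t-based calculation gives 16.7, so 17. The stated size fits a standardised difference of about 0.99 to 1.0.

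**2. Why group size matters.** Set the control SD to 1 and the BFR SD to r. The pooled test estimates the variance of the mean difference as s² × (1/n₁ + 1/n₂), where s² has expectation [(n₁ − 1)r² + (n₂ − 1)] / (n₁ + n₂ − 2). The true variance is r²/n₁ + 1/n₂.

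- 17 v 17, r = 1.5: pooled 1.625 × 2/17 = 0.191; true 3.25/17 = 0.191. No error.
- 10 v 17, r = 1.5: s² = (9 × 2.25 + 16)/25 = 1.45; pooled 1.45 × 0.1588 = 0.230; true 0.225 + 0.0588 = 0.284. The standard error is too small by a factor √(0.230/0.284) = 0.90.
- 10 v 17, r = 0.67: s² = (9 × 0.449 + 16)/25 = 0.802; pooled 0.127; true 0.0449 + 0.0588 = 0.104. The standard error is too large by a factor of about 1.11.

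**3. Simulation of the two-step rule.** Assumptions: normal data, two-sided 5%, F pre-test at 5%, pooled t if it does not reject and Welch t if it does. Control n = 17; 100,000 trials per setting, so the Monte Carlo standard error is about √(0.05 × 0.95/100,000) = 0.07 point. SD ratio is BFR over control.

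| BFR n | F test detects ratio 1.5 | Detects ratio 2 | Type I error, ratio 1.5 | Ratio 2 | Ratio 0.67 | Ratio 0.5 |
|---|---|---|---|---|---|---|
| 17 | 34.5% | 77% | 5.0% | 5.0% | 5.0–5.1% | 5.0–5.1% |
| 15 | 33.5% | 74% | 5.3% | 5.2% | 4.8% | 4.8% |
| 14 | 32.5% | 73% | 5.7% | 5.5% | 4.6% | 4.7% |
| 13 | 31.4% | 71% | 5.7% | 5.6% | 4.4% | 4.6% |
| 12 | 30.9% | 70% | 5.9% | 5.7% | 4.2% | 4.5% |
| 10 | 28.7% | 65% | 6.5% | 6.4% | 3.9% | 4.1% |

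Repeat runs of 200,000 trials gave 5.4–5.5% at 14 v 17, 5.8–6.0% at 12 v 17 and 6.4–6.6% at 10 v 17 for ratios 1.5 to 2. With equal SDs the rule stays at 5.0 to 5.1% at every split. Welch used throughout gives 4.9 to 5.1% in every setting of the table.

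**4. Sensitivity to the unspecified parts.** With Brown-Forsythe as the pre-test and Welch as the fallback, 10 v 17 gives 7.0% and 7.4% at ratios 1.5 and 2. With an F pre-test and Wilcoxon as the fallback, it gives 7.1% and 8.3%; at 17 v 17 that version gives 5.3% and 5.8%.

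**5. How unequal the groups might be.** Under simple randomisation (assumed), 34 patients split 14/20 or worse with probability 2 × P(Bin(34, 0.5) ≤ 14) = 0.39. Reaching 10 v 17 by withdrawal alone means losing 7 of 17 BFR patients (41%) and no controls.

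**The case against.** The strongest reply is that the plan targets equal groups, where the rule is harmless, and that unequal numbers alone do nothing. Inflation needs unequal groups, unequal variances, and the larger variance in the smaller group, all together. Nothing in the documents says the BFR group will be the more variable, and in the reverse case the rule is conservative. Heavy one-sided loss is also unsupported: Section 2 already excludes patients who cannot tolerate BFR, and Section 4 expects few complications. An F test followed by Welch is itself an assumed reading. All of this stands, and it limits the point to a modest departure that could go either way.

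A reader might infer that the stated 5% rate is in fact exceeded under this plan. The documents do not support that, since they give neither SDs by arm nor a withdrawal rate. A reader might also apply the calculation within the operative and nonoperative arms, where error reaches about 7.3% at 6 v 9 and 8.6% at 5 v 9 (SD ratio 2). But Section 3 describes one BFR-control comparison with 17 per group and states no within-arm test. Nor is it stated whether the 34 cover both arms.

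Two further objections hold. It would be too broad to say that the pre-test has little power, because at 17 v 17 the F test finds an SD ratio of 2 in 77% of trials. And where one-sided withdrawal is real, selection bias from the destroyed data matters more than a point or so of type I error.

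What survives is that the rule is unspecified, often misses a moderate variance difference, and has a better replacement.

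**Conclusion.** The point holds as a cheap improvement, not as a demonstrated error. At 17 v 17 the two-step rule with a Welch fallback keeps 5%.

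If the BFR group ends up smaller and the more variable (SD ratio 1.5 to 2), type I error is about 5.3 to 5.6% at 14 or 15 v 17, 5.8 to 6.0% at 12 v 17 and 6.4 to 6.6% at 10 v 17. If the smaller group is the less variable, it is about 4% at 10 v 17. These figures assume normal data, an F pre-test at 5% and a pooled or Welch t test after it. The group sizes and SD ratios are also assumed.

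The direction cannot be known in advance and can differ by outcome, so it does not follow that every p-value would be too favourable. The gap in the text, a gate with no named test, level or consequence, needs no assumption.

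**What to change.** In Section 3, delete the variance pre-test and state that all two-group comparisons of continuous data will use the Welch (unequal-variance) t test, two-sided at 5%. The rule for non-normal data is a separate matter and need not change for this point.

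**What it gains.** Welch stays between about 4.7 and 5.5% in every setting examined, including groups as small as 5 v 9. It also removes an undefined choice of test.

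**What it costs.** One sentence. With equal variances and a standardised difference of about 1, power is 80.7% against 80.8% for the two-step rule at 17 v 17, and 66.0% against 67.2% at 10 v 17. At 8 v 9 it is 47.1% against 48.0% for the pooled test. When the smaller group is the more variable, nominal power is also lower: 48.0% against 51.1% at 12 v 17 with SDs of 22.5 and 15. Part of that gap is the two-step rule's inflated error.

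**What it leaves open.** Welch does nothing about bias from withdrawing BFR-intolerant patients and destroying their data. That needs its own correction.

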4. ANTICIPATED RISKS

Patients may experience discomfort from the blood flow restriction (BFR) cuffs. Previous studies have shown that prolonged tourniquet use can lead to pain, nerve injury, and swelling. Recent advancements in tourniquets have resulted in complication rate of .04-.08% when used during orthopedic surgeries.⁴ Recent studies specifically on use of tourniquets for BFR have found very low complication rate and we will be using the tourniquet for a very short duration of time. There is concern that BFR may increase the risk of DVT, however multiple studies have shown that BFR does not increase thrombin clot

generation in in-vivo models.^{1,3} Regardless, in order to minimize risk we will exclude patients with a history or family history of DVT. Additionally, patient information will be kept de-identified on a password protected henry ford computer for the duration of the project. There is a minimal risk of privacy breach as only individuals who would regularly be involved in the peri-operative care of an RC tear patient will be included in the study.

5. ANTICIPATED BENEFITS

- Potential benefits include faster return to play following RCR, less pain following surgery, better ROM and a better overall satisfaction and result following RC tear and reconstruction.

6. RENUMERATION/COMPENSATION

- No compensation offered

7. COSTS

- Additional costs will primarily be focused on obtaining the pressure cuffs. The payment for this will be provided by the investigators. Additionally, there will be some time cost to train the patient and physical therapists on use of the cuffs, however this will be minimal additional time and voluntary. There are no additional monetary costs.

8. ALTERNATIVES

Patients do not have to participate in this study and are able to undergo typical physical therapy as is the current standard.

9. CONSENT PROCESS AND DOCUMENTATION

Consent will be obtained from patients to participate in this investigation. We will obtain consent during a preoperative clinic visit. All research personnel listed in the IRB including the PI and associates will be responsible for informed consent. This will be done at the end of clinic visits to ensure there is ample time to answer questions. Additionally, contact information will be provided for questions throughout the entire process. Consent or lack thereof to participate will in no way affect the level of care provided for each patient. If at any point the patients no longer wish to participate, they will be placed back into the usual post-operative care pathway. Minors will be consented along with their parents and either patient or parent may elect to participate or withdraw from the study. Patients will all be English speaking and have capacity to self-consent. Documenting consent will be done during the clinic visit. Documentation will be stored in a locked room and kept in a folder with no visible identifying information.

Information will be kept in a locked area only accessible to study personnel. This will be kept in folders so there is no visible identifying information. The results of questionnaires and functional tests will be kept on a password protected HF computer and there will be no identifying information aside from MRN kept on these forms. All data will be destroyed following publication of this study or after six months of inactivity.

10. WITHDRAWAL OF SUBJECTS

- Subjects will be withdrawn from the study if they are unable to tolerate the BFR therapy. Additionally, if they suffer from any complications of the therapy they will be withdrawn immediately. This will be facilitated by describing the reasons for withdrawal to the patient prior to initiating the study and ask patients and other providers to inform the investigators if there are any issues or concerns.

- Data collection on patients who were withdrawn will be terminated and data destroyed.
- Patients may withdraw from the study at any time for any reason without affecting the quality of their care

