Patients undergoing operative rotator cuff repair (RCR) will undergo preoperative rehabilitation prior to surgery for two weeks. Due to limitations of health insurance coverage of physical therapy sessions, the two weeks of preoperative "prehab" will consist of a structured home exercise program that is taught to the patient by a physical therapist during one session and recorded on a physical therapy (PT) diary by the patient during the two weeks leading up to surgery. Patients will be provided with video instruction and training on how to conduct the exercises and this will also be done with and without the use of BFR depending on group allocation (via randomization). Additionally, warning signs for BFR cuff intolerance such as increased pain, swelling, numbness/tingling of the arm will be communicated to the patient. Following surgery patients will immediately be started in a formal physical therapy regimen as an outpatient. Therapy will consist of a structured program progressing from range of motion to strength training and then functional tests. Patients will remain in their allocated BFR or non-BFR group.

Protocol as follows, both groups will use the same protocol with the only difference being use of BFR:

For surgical patients:

- Preop: Patients will undergo a home program consisting of isometric exercises including shoulder extension, abduction, external rotation and internal rotation pushing against a wall.

For both surgical and non-surgical patients:

- Post-op weeks 0-8: Passive shoulder range of motion (ROM) only
- Sling immobilization with active elbow, wrist and hand ROM
- Passive ROM only of shoulder including pendulums, supine elevation in scapular plane, external rotation with arm at side.

8-12 weeks being more active range of motion

- Discontinue sling
- Being active exercises including prone row, standing internal/external rotation with bands, wall slides into shoulder flexion

Weeks 12-20: Strength and function of Side lying shoulder external rotation, increase resistance band exercises

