12. DATA AND SAFETY MONITORING PLAN

We will be consistently checking in on patients' safety as they undergo the usual post-operative RCR protocol. This will involve clinic visits in which we monitor the PT progress as well as the patient's adherence to the protocol. We will also be in weekly communication with therapists regarding patient progress and ability to complete protocol.

Unanticipated Problems and Adverse Events

We will report any problems or adverse events to the IRB via email

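### Section 10 withdraws randomised patients for BFR intolerance or a therapy complication and destroys their data, so the as-randomised comparison is lost once anyone is removed

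*Combined protocol and SAP*

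**What the plan says.** Section 3 (Study Procedures) sets the order of events. Treatment is chosen as operative or nonoperative, consent and baseline testing follow, and then: "Within each arm, patients will be randomized via computer to be placed in either the blood flow restriction (BFR) cohort" or the non-BFR cohort. The rehabilitation protocols are otherwise identical, "with the only difference being the use of a BFR cuff during rehabilitation for the BFR cohort". For surgical patients, BFR begins after allocation, in the two-week home programme. There patients are told of "warning signs for BFR cuff intolerance such as increased pain, swelling, numbness/tingling of the arm".

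Section 10 (Withdrawal of Subjects) has two mandatory triggers. The first reads "Subjects will be withdrawn from the study if they are unable to tolerate the BFR therapy". The second says that "if they suffer from any complications of the therapy they will be withdrawn immediately". Patients may also withdraw by choice. For all of them, "Data collection on patients who were withdrawn will be terminated and data destroyed". No exception is made for baseline or earlier visits.

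The analysis text in section 3 specifies two-group t tests, chi-square tests, nonparametric equivalents and a multivariable regression. It names no analysis set, no follow-up after treatment is stopped, no missing-data method and no allowance for dropout. Secondary outcomes include "Pain via visual analogue scale (VAS) pain scale at each visit". On safety, section 12 says "We will report any problems or adverse events to the IRB via email".

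**The concern.** The plan treats stopping the cuff and leaving the study as one event. A control patient cannot be intolerant of a cuff that he or she does not wear, so the first trigger selects patients in one randomised group by their response to treatment and has no counterpart in the other. The second trigger, and voluntary withdrawal, can occur in both groups.

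Three things are at stake.

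- **Comparability.** After any intolerance withdrawal, the BFR group consists of patients who tolerated BFR, and it is compared with all remaining controls. This affects strength, range of motion, pain, patient-reported outcomes and ultrasound findings alike. If the removed patients would have done worse, the comparison favours BFR.
- **Pain.** Increased pain is a listed sign of cuff intolerance, and VAS pain is an outcome. Patients with cuff-related pain may therefore drop out of the pain comparison.
- **Harm.** No harm outcome or by-group harm report is planned, so the study dataset would lose the patients who tolerated BFR worst.

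A vague analysis plan can be repaired before the data are analysed. Destroyed data, and measurements never taken, cannot be.

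**Working it through.** **Inputs from the plan (section 3, data analysis).** Target difference 15 points of work deficit; power 80%; alpha 0.05; 17 per group, 34 in all. No SD, dropout rate or intolerance rate is given, and the test is not said to be one- or two-sided.

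**The plan's own figure.** The sample size of 34 cannot be reproduced without an SD, so it was solved backwards. For a two-sided t test at 17 v 17, the noncentral t distribution gives 80% power at a standardised difference d = 0.991. Hence SD = 15 / 0.991 = 15.1 points. This value only sets the scale below; the concern does not depend on it.

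**Model for the rule.** Assume that a share p of patients in each group is latently intolerant and would have a deficit g SD larger. Only the intolerant patients in the BFR group are deleted. Controls keep theirs, so with no true treatment effect the expected spurious difference is

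bias ≈ p × g × SD.

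Example: 0.20 × 1 × 15.1 = 3.0 points, which is 3.0 / 15 = one fifth of the target difference. Error rates come from 200,000 simulated trials per scenario, 17 per group, no true effect, pooled t test.

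| p | g | Bias (points) | Two-sided error |
|---|---|---|---|
| 5% | 0.5 | 0.4 favouring BFR | 5.0% |
| 10% | 0.5 | 0.8 favouring BFR | 5.2% |
| 20% | 0 | none | 5.0% |
| 20% | 0.5 | 1.5 favouring BFR | 5.8% |
| 20% | 1 | 3.0 favouring BFR | 7.7% |
| 30% | 1 | 4.5 favouring BFR | 10.6% |
| 20% | −0.5 | 1.5 against BFR | not tabulated |

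At p = 20% and g = 1, false-positive results in favour of BFR occur 7.1% of the time, against a nominal 2.5%. Repeat runs agree to within about 0.1 of a percentage point. Keeping all randomised patients in the same scenario gives a bias of 0.0 points and an error of about 5%.

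**A second model.** A fixed number of BFR patients is removed, and removal is correlated (rho) with a larger deficit. With 3 of 17 removed, rho of 0.3, 0.5 and 1.0 gives a spurious difference of 1.3, 2.2 and 4.5 points in favour of BFR, with two-sided error of 5.6%, 7.3% and 15.5%. At rho = 0 the error stays at about 5%.

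**Chance that the comparison is affected at all.** P(at least one of 17 removed) = 1 − (1 − p)^17. This is 16% at p = 1%, 58% at 5%, 83% at 10% and 98% at 20%.

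**Power.** With d = 0.991, power falls from 80% to 78.7% at 17 v 16 and to 75.6% at 17 v 14.

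**The case against.** The strongest case against is about size.

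- **Events may be rare.** Section 2 already excludes patients unable to tolerate BFR. Section 4 cites a complication rate of .04-.08% for surgical tourniquets and a very low rate for BFR. At .04-.08%, the chance of any complication among 17 patients is 1 − 0.9996^17 = 0.7% to 1 − 0.9992^17 = 1.4%. This stands for the complication trigger, so far as surgical tourniquet figures carry over. It does not settle intolerance, which is a lower threshold than a complication. Section 2 describes screening by chart, history and questions, with no trial of the cuff, and sections 3 and 10 themselves provide for intolerance after allocation.
- **The bias is small at low rates.** At 5-10% intolerant and 0.5 SD worse, the error hardly moves. Clear inflation needs roughly one patient in five removed with a full SD worse prognosis. This stands.
- **The scale is borrowed.** The SD is back-solved, and the power paragraph speaks of legs in a shoulder trial. It is also unclear whether 17 per group is pooled or applies within each of the operative and nonoperative arms. This stands, and it changes the illustrative figures but not the reading of section 10.
- **Some data may survive.** Section 11 says that patient data may be in the chart, and adverse events go to the IRB. True, but the protocol gives no route for using chart data from withdrawn patients, and study measurements after withdrawal would not exist.
- **The pain overlap is indirect.** No VAS value triggers withdrawal. Correct; the overlap runs through pain as a listed sign of intolerance.

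Section 13 was not in the text available for review, so statements that something is absent apply to the remaining sections.

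**Conclusion.** The concern holds, and it should be fixed before the trial proceeds. Section 10 is an explicit rule, not a gap in detail, and following it gives a worse trial than the obvious alternative. It filters one randomised group by tolerance of the treatment and destroys the study data that could show whether this mattered.

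The case rests on that principle and on irreversibility, not on a demonstrated bias. Over the assumed range of 5-30% intolerant and 0 to 1 SD worse, the bias runs from zero to 4.5 points in favour of BFR and the two-sided error from 5.0% to 10.6%. If intolerant patients would have done better, the bias goes against BFR. The loss of power is minor. If nobody is withdrawn, the comparison is unaffected.

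**What to change.** Leave the treatment-stopping rule in section 10 as it is, and separate stopping BFR from leaving the study. State that:

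1. a patient who stops BFR stays in the study unless he or she withdraws consent;
2. data already collected are kept unless the patient withdraws consent for their use;
3. with consent, outcomes continue to be measured at the scheduled clinic visits;
4. all patients are analysed in the group to which they were randomised;
5. intolerance, complications and withdrawals, with reasons, are reported by randomised group.

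An analysis restricted to patients who tolerated BFR may be kept as secondary. In section 2, add a phrase making clear that the listed exclusions apply before randomisation.

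The cost is the edits to sections 10 and 2, matching consent-form and IRB wording on data retention and continued measurement, and a few more dynamometer and ultrasound measurements in patients who stopped BFR. No extra patients or visits are needed. There are two downsides. The estimated effect may be diluted by patients who stopped BFR, and those who decline further measurement will still have missing data.

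### Patients who cannot tolerate BFR, or have a complication of it, are withdrawn and their data destroyed, so the retained dataset holds no recognised case, and no by-group safety summary is planned

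*Combined protocol and SAP*

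**What the plan says.** Section 10 (Withdrawal of Subjects) has two triggers that the investigators apply. The first is "Subjects will be withdrawn from the study if they are unable to tolerate the BFR therapy". The second is that "if they suffer from any complications of the therapy they will be withdrawn immediately". The investigators are to learn of cases because they will "ask patients and other providers to inform the investigators if there are any issues or concerns". The consequence follows: "Data collection on patients who were withdrawn will be terminated and data destroyed". A patient's own choice to leave is covered by a separate line.

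Section 3 (Study Procedures) sets the context. "Within each arm, patients will be randomized via computer to be placed in either the blood flow restriction (BFR) cohort" or the conventional cohort, and the cuff is the only intended difference between the two. For surgical patients, "Patients undergoing operative rotator cuff repair (RCR) will undergo preoperative rehabilitation prior to surgery for two weeks". This is a home programme taught in one session and "recorded on a physical therapy (PT) diary by the patient during the two weeks leading up to surgery", with or without the cuff according to allocation. The plan expects that some patients may not tolerate it: "warning signs for BFR cuff intolerance such as increased pain, swelling, numbness/tingling of the arm will be communicated to the patient".

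The outcomes in Section 3 are strength, range of motion, VAS pain, patient-reported scores and ultrasound measures of muscle. None is a complication or tolerability outcome. The analysis text gives generic tests for continuous and categorical data and names no safety variable. Section 12 provides clinic visits, weekly contact with therapists and emailed reports of adverse events to the IRB. It describes no tabulation by group.

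**The concern.** The rule removes the patients who would supply this trial's own evidence on whether the cuff is tolerated. Section 4 names nerve injury, swelling, pain and a concern about DVT, and takes its reassurance from other studies. If recognised cases leave the dataset and their follow-up stops, the trial cannot add to that evidence from its retained data. A later nerve or vascular event in a withdrawn patient would not be recorded as study data, even if it were charted clinically.

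The loss is also one-sided. Only a BFR patient can fail to tolerate BFR, so that trigger acts in one randomised group. The operative arm is exposed early, because the cuff is used at home for two weeks before the first post-operative visit.

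**Working it through.** **The rule, step by step.**
1. Intolerance, or any complication of the therapy, leads to mandatory withdrawal (Section 10). No severity threshold is given and complication is not defined, so a patient with mild, tolerated symptoms might stay in.
2. Withdrawal ends data collection (Section 10).
3. The data are destroyed (Section 10). Nothing is exempted: not adverse-event records, the reason for stopping, or data already collected.
4. Hence a recognised case cannot remain in the retained dataset, whatever the true rate.
5. The outcome list and analysis text (Section 3) and the monitoring plan (Section 12) contain no by-group safety summary. Section 13 was not available to us.

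**What one withdrawal costs.** Section 3 schedules four visits: pre-operative, 2 weeks, 6 weeks and three months. An operative patient withdrawn during prehabilitation loses all three post-operative visits. The baseline data are destroyed as well, so nothing from that patient is retained.

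**How often it might happen.** Inputs:
- n = 17 BFR patients (Section 3). The plan's 34 (17 per group) cannot be reproduced, because no standard deviation is stated. It is used here only as a count.
- p = 0.04% to 0.08%, the only complication rate in the plan (Section 4). It is for tourniquets during orthopedic surgery, not BFR.
- p for BFR intolerance is not given. The rates of 5%, 10% and 20% below are assumptions.

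Formulas: expected number removed = n × p; chance of at least one = 1 − (1 − p)^n.

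| Rate p | Expected of 17 | Chance of at least one |
|---|---|---|
| 0.04% (quoted) | 0.007 | 1 − 0.9996^17 = 0.7% |
| 0.08% (quoted) | 0.014 | 1 − 0.9992^17 = 1.4% |
| 5% (assumed) | 0.85 | 1 − 0.95^17 = 58% |
| 10% (assumed) | 1.7 | 1 − 0.90^17 = 83% |
| 20% (assumed) | 3.4 | 1 − 0.80^17 = 98% |

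If the 17 per group is meant to apply separately in the operative and nonoperative arms, there would be 34 BFR patients. The chances become 1.4-2.7% at the quoted rates and 83%, 97% and 99.9% at the assumed ones.

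**What full retention would give.** With no event among 17, the exact two-sided 95% upper limit is 1 − 0.025^(1/17) = 19.5%. The information is modest even when nothing is destroyed.

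**The case against.** **Records survive elsewhere.** Section 12 requires adverse events to be reported to the IRB and makes no exception for withdrawn patients. It also provides weekly therapist contact. Section 11 allows for data in the chart and for authorised access to it. A reader might infer that all trace of harm is lost, and the documents do not support that. What stands is narrower: no analysis plan uses these sources, and nothing says that reports will be tabulated by randomised group.

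**The trial is small, and it is about strength.** It promises no complication rate, and 17 patients cannot exclude even a fairly common problem. That is true, and it rules out a formal safety comparison. It does not justify discarding the few cases that occur.

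**Intolerant patients are already excluded.** Section 2 lists inability to tolerate BFR among the exclusions. It does not say when this is judged, and Section 10 plainly expects intolerance to arise during therapy. If the criterion were applied after randomisation, it would be a second route for removing the same patients.

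**Withdrawal protects patients.** Stopping the cuff protects them. Ending follow-up and destroying records adds no protection from the cuff.

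**Conclusion.** The point holds as a statement about the retained study dataset. Section 10 removes every recognised case of BFR intolerance or complication, mainly from the BFR group, and no available section plans a by-group safety summary. This should be changed, although it does not make the plan unworkable.

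The size depends on a rate that the plan does not give. For complications, at the quoted surgical rate, the rule would seldom operate (0.7-1.4% chance of any case among 17). For intolerance, at assumed rates of 5-20%, it would remove 0.9 to 3.4 of 17 on average, with a 58-98% chance of at least one. These figures do not show that intolerance is likely; they show what follows if it occurs at those rates.

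Two stronger readings are not supported:
- A reader might infer that the trial will publish a falsely clean complication rate. The plan contains no safety table in which such a rate would appear, and the gap between patients randomised and analysed could itself reveal the losses.
- A reader might measure the loss in rehabilitation weeks: 20 of 22 after prehabilitation. Study measurements are taken at visits that end at three months, and the rule destroys all of the patient's data, so a share of weeks is the wrong measure.

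**What to change.** 1. **Section 10.** Replace withdrawal for intolerance or complication with stopping BFR while scheduled visits continue. If the patient withdraws consent, keep the data collected up to that date, including adverse events and the reason for stopping, subject to consent.
2. **Section 2.** State that the exclusion for inability to tolerate BFR applies only before randomisation.
3. **Section 3, outcomes and data analysis.** Add one descriptive table by randomised group. It should show patients with adverse events, including nerve injury and DVT, and, in the BFR group, patients who stopped BFR. Use all randomised patients as the denominator and give exact 95% confidence intervals. The existing visits, weekly therapist contact and IRB reports can supply the data.

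The cost is a short IRB and consent amendment, a few extra visits for patients who stop BFR, and one table. The intervals will be wide: 0 of 17 still allows up to 19.5%. The change is best made before any patient is withdrawn under the present rule, because destroyed data cannot be recovered.
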